13.2 GLM

GLMs will include treatment group as a main effect and the randomization stratifiers and an appropriate baseline value (if applicable) as covariates. Model-based LS means and SEs will be reported for each treatment group, along with a p-value for the treatment group comparison.

Model assumptions will be evaluated using diagnostic tools such as Q-Q and scatter plots of residuals, and sensitivity analyses using alternative methods (e.g., rank-based) will be considered if there appear to be substantial deviations from model assumptions. Outlier assessment will be done using visual inspection (e.g., box-and-whisker plots) and potential outliers will be investigated for data entry accuracy and biological consistency. If unexplainable outliers are present, a sensitivity analysis may be done excluding the outliers to assess their effect on the analysis conclusion.

13.3 Missing Observations

For the primary efficacy analysis, multiple imputation will be used for missing observations with only treatment group included in the imputation model; ie, the observed within-treatment-group Bernoulli distribution of response will be the distribution from which random values are drawn to replace missing observations. The number of imputations will be the percentage of subjects with missing data, rounded up to an integer. Results from multiple imputations will be combined using the Rubin method.⁸ A complete-case sensitivity analysis will also be done, whereby for each endpoint only subjects with complete data are included. For secondary endpoints, only complete-case analyses will be done.

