### 9.4.1 Efficacy Analyses

The analysis of the primary efficacy endpoint family will compare the 2 treatment groups (OP0201, placebo) with respect to the proportion of Participants with no bulging of the TM at the Day 4 Visit as well as the proportion of Participants with no MEE at the Day 12 Visit using the ITT population for which Participants with missing data at the Day 4 Visit will be considered as having bulging TM and those with missing data at the Day 12 Visit will be considered as having MEE. A sensitivity analysis will be done that defines the endpoints as no bulging of the TM at the Day 4 Visit and no recurrence of bulging TM throughout the remainder of the study, and no MEE at the Day 12 Visit and no recurrence of MEE throughout the remainder of the study. Sensitivity analyses will also be done using the per-protocol population. Treatment groups will be statistically compared using generalized estimating equations (GEE), if possible, with an alternative method (eg, logistic regression) at each visit as an alternative if GEE convergence cannot be achieved. Randomization stratifiers (daycare attendance [yes, no] and age group [ $\geq 6$  to  $<12$  months,  $\geq 12$  to  $\leq 24$  months]) and degree of TM bulging at baseline will be covariates. Tympanic membrane bulging at baseline will also be evaluated as a potential effect modifier.

The step-up Hochberg procedure will be used to control the familywise Type 1 error. Specifically, the endpoint with the highest p-value will be tested first at the 0.05 significance

level and, if significant, both endpoints will be declared significant; if the endpoint with the highest p-value is not significant at the 0.05 level, the other endpoint will be tested at the 0.025 significance level. A positive treatment effect on efficacy will be concluded if at least 1 of the 2 endpoints in the primary efficacy endpoint family is significant

Descriptive statistics will be provided for the primary efficacy endpoint family by the following sub-groups: age stratum ( $\geq 6$  to  $< 12$  months,  $\geq 12$  to  $\leq 24$  months), race (Caucasian, non-Caucasian), gender (male, female), laterality of disease (unilateral, bilateral), history of recurrent AOM defined as 3 or more episodes in the preceding 6 months or 4 or more episodes over the course of 12 months (yes, no), and daycare attendance stratum defined as exposure to 3 or more children outside of the home for 10 or more hours per week (yes, no).

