5. SAMPLE SIZE AND POWER

The power calculation is based on a 2-sided Pearson chi square test of each of the two endpoints in the primary efficacy endpoint family and control of type 1 error using the step-up Hochberg procedure.⁸ The minimally important difference in proportions for both endpoints is approximately 0.25. With 70 subjects randomized per treatment group, an assumed dropout rate of 10%, and using multiple imputation as described in Section 13.3, this study will have 93% power to detect a treatment effect in at least one of the two endpoints assuming 40% of placebotreated subjects will have no bulging TM at Day 4 and 30% of placebotreated subjects will have no MEE at Day 12. A summary of sample size requirements is as follows:

Total N	Power
100	82%
102	82%
120	88%
132	91%
140	93%

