12.2 MEE

Otoscopy will be performed at each study visit (as well as 30 minutes post-dose on Day 1, for safety only) to evaluate the presence/absence of MEE; each ear will be evaluated separately, and a listing will show presence/absence of MEE for each ear separately.

Endpoints

No MEE at the Day 12 visit is one of two endpoints in the primary efficacy endpoint family (see Section 13.5). The following sensitivity analyses will be done:

- PP analysis population
- Complete case (ie, mITT subjects who completed the Day 12 visit; see Section 13.3)
- Complete case with the endpoint defined as no MEE at the Day 12 visit and no recurrence of MEE throughout the remainder of the study. In this instance, "complete case" is equivalent to mITT subjects who completed the Day 28 visit.

The hypothesis set to be tested is:

 H_o : $P_A = P_P$ vs. H_A : $P_A \neq P_P$

Confidential Page 23 of 35

where P_A and P_P are the population proportions for OP0201 and placebo, respectively, for no MEE 12 days after the start of a 10-day treatment regimen.

No MEE at the Day 4 and Day 28 visit are secondary endpoints.

Summaries and Analyses (see Section 13)

No MEE will be summarized and analyzed separately by visit using logistic regression. Summary tables will include frequencies and percentages of no MEE for each treatment group by visit and p-values for the differences. Crude rates of no MEE by treatment group and visit will be graphically displayed using bar charts.

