13. STATISTICAL METHODS

13.1 Logistic Regression

Logistic regression models will include treatment group as a main effect and the randomization stratifiers (age group, daycare attendance) and an appropriate baseline value (if applicable) as covariates. Model-based LS means and SEs will be reported for each treatment group, along with a p-value for the treatment group comparison. For sparse data, two-sided Fisher's exact tests will be used (ie, with no covariate adjustment).

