13.4 Multiplicity

The familywise type 1 error rate for the primary efficacy endpoint family will be 0.05 and will be controlled using the Hochberg procedure. Specifically, the p-value of the endpoint with the highest p-value will be compared against the 0.05 significance level and, if significant, both endpoints will be declared significant; if the endpoint with the highest p-value is not significant at the 0.05 level, the other endpoint will be tested at the 0.025 significance level. A positive treatment effect on efficacy will be concluded if at least one of the two endpoints is significant.

Confidential Page 27 of 35

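### Imputing the primary endpoints on treatment group alone, with about ten unseeded imputations and only a complete-case check, leaves borderline verdicts seed-dependent and worse-than-observed dropout untested

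*SAP*

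**What the plan says.** SAP 13.3 governs missing outcomes for both primary endpoints (no bulging at Day 4, no MEE at Day 12). It says "multiple imputation will be used for missing observations with only treatment group included in the imputation model", with values drawn from the response rate observed in each arm and results pooled by Rubin's method. On the number of draws: "The number of imputations will be the percentage of subjects with missing data, rounded up to an integer". No seed appears in the SAP text. SAP 5 bases its 93% power on "an assumed dropout rate of 10%, and using multiple imputation as described in Section 13.3".

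The analysis model in SAP 13.1 is richer than the imputation model. It includes "the randomization stratifiers (age group, daycare attendance) and an appropriate baseline value (if applicable) as covariates".

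The check on missing data in SAP 13.3 is this: "A complete-case sensitivity analysis will also be done, whereby for each endpoint only subjects with complete data are included". SAP 12.1 and 12.2 list the same complete-case analysis, a per-protocol analysis, and a complete-case version with a no-recurrence endpoint.

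Protocol 9.4.1 had a different rule: "Participants with missing data at the Day 4 Visit will be considered as having bulging TM", and likewise missing at Day 12 counted as MEE. SAP 16 declares that multiple imputation replaces this rule. It does not keep the rule as a sensitivity analysis.

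Under the Hochberg procedure in SAP 13.4, if the larger p-value misses 0.05, "the other endpoint will be tested at the 0.025 significance level".

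**The concern.** There are three linked weaknesses.

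- **Few imputations, no seed.** With about 10 imputations the pooled p-value carries visible Monte Carlo noise. Two analysts who both follow the SAP on the same data can land on opposite sides of 0.025 or 0.05, and trial success can rest on one such comparison. The SAP also does not say whether the percentage missing is taken per endpoint or overall, so the number itself is open.
- **Thin imputation model.** It leaves out covariates that the analysis model uses. For Day 12 it also ignores the child's Day 4 otoscopy, which is the nearest earlier measurement.
- **A check that barely tests the assumption.** Complete case and treatment-only imputation both take missing children to respond much like observed children in their arm. If children still bulging at Day 4 leave more often, and more so in one arm, both analyses move the same way and their agreement does not reassure.

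The study is an exploratory Phase 2a. At stake are a reproducible verdict and a fair reading of dropout.

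**Working it through.** **Inputs.** From SAP 5: 70 per arm, 10% dropout (so 63 observed and 7 missing per arm), placebo rates 0.40 and 0.30, difference 0.25. From SAP 13.4: limits 0.05 and 0.025. From SAP 7: the first 3 children dosed are excluded, so about 137 remain if 140 are randomized.

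**The SAP's own figure.** Simulating 63 completers per arm, chi-square tests, Hochberg and independent endpoints gives 93.3% power, against 93% stated. Using the SAP's imputation itself with 10 draws gives 93.1%. The power figure is not in dispute.

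**Number of imputations.** M = ceil(100k/137) for k missing. For k = 1, 2, 3, 7, 14 this gives M = 1, 2, 3, 6, 11 (10 for 14 of 140). With M = 1 the between-imputation variance is undefined. That is very unlikely at 10% dropout: 137 × 0.1 × 0.9^136 = 8 × 10^-6.

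**Seed spread, unadjusted, 38/63 v 25/63.** The complete-case p is 0.0205.

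- Log odds ratio: Q = 2 × ln(38/25) = 0.837, because 38 = 63 − 25.
- In each arm p(1 − p) = (38 × 25)/63² = 0.2394.
- Within-imputation variance: U ≈ 2/(70 × 0.2394) = 0.1194.
- Between-imputation variance: B ≈ 2 × 7/(70² × 0.2394) = 0.0119.
- Rubin total at M = 10: T = U + (1 + 1/10)B = 0.1325, standard error 0.364.
- Seed-to-seed SD of Q: √(B/10) = 0.0345.
- So z ≈ 2.30 ± 1.96 × 0.0345/0.364 = 2.30 ± 0.19, or p from about 0.013 to 0.035.

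Direct simulation also lets the estimated B vary:

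| Observed data | M | Central 95% of p over seeds | Seeds above 0.025 |
|---|---|---|---|
| 38/63 v 25/63 | 10 | 0.012–0.037 | about 29% |
| 38/63 v 25/63 | 100 | 0.0175–0.0247 | about 2% |
| 38/63 v 25/63 | 500 | 0.019–0.022 | 0% |
| 41/63 v 25/63 (design effect) | 10 | 0.002–0.010 | practically none |

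A second example, 36/63 v 24/63 (complete-case p 0.033), runs from 0.021 to 0.051 (5th to 95th percentile) at M = 10, across both Hochberg limits.

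**Hochberg verdict over whole trials.** This uses the planned covariate-adjusted logistic model. Assumptions: age stratum 50/50, daycare 40%, baseline bulging grades 30/40/30% with coefficient −0.8 per grade, latent correlation 0.5 between endpoints, 7 per arm missing at random on both. The table shows how often two seeds disagree.

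| True effect | M = 10 | M = 100 |
|---|---|---|
| 0 | 1.7% | 0.5% |
| 0.17 | 5.3% | 1.6% |
| 0.25 | 2.4% | 0.7% |

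Among trials whose smaller complete-case p lies between 0.015 and 0.04, 22–28% disagree at M = 10 and about 9% at M = 100. Familywise type I error at M = 10 is 4.6%.

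**Omitted covariates, random missingness.** With an assumed baseline effect of 0.8–1.2 per grade, the baseline coefficient shrinks by 11–12% and the treatment log odds ratio by 2–4%. Hochberg success at 0.25 is 90.6%, against 91.6% for adjusted complete case.

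**Day 12 dropout related to Day 4 bulging, no true effect.** Assumptions: Day 4 response 0.40, Day 12 response 0.30, phi 0.5 between them, dropout 3% in children not bulging, overall dropout 13% v 7% with OP0201 higher.

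- Covariance: 0.5 × √(0.4 × 0.6 × 0.3 × 0.7) = 0.112. Day 12 response is 0.30 + 0.112/0.4 = 0.581 if not bulging at Day 4 and 0.30 − 0.112/0.6 = 0.113 if bulging.
- Dropout if bulging: (0.13 − 0.4 × 0.03)/0.6 = 0.197 on OP0201 and (0.07 − 0.012)/0.6 = 0.097 on placebo.
- Observed rate, OP0201: (0.4 × 0.97 × 0.581 + 0.6 × 0.803 × 0.113)/0.87 = 0.3215.
- Observed rate, placebo: (0.4 × 0.97 × 0.581 + 0.6 × 0.903 × 0.113)/0.93 = 0.3080.
- Spurious difference: 1.35 points. With phi 0.3 it is 0.8 points.

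For phi 0.3–0.5 the odds ratio is 1.04–1.06 in adjusted complete case, 1.04–1.07 in treatment-only imputation, and 1.00 when Day 4 status is imputed on. At phi 0.5, false positives favouring OP0201 (nominal 2.5%) are 3.7% in both planned analyses and 2.9% (SE 0.3) with Day 4 status, stratifiers and baseline in the imputation. At an assumed extreme of 16% v 8% they are 4.1–4.3% and 2.3%. Equal dropout gives no bias.

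**Dropout related to baseline severity.** With assumed response 0.6/0.2 by severity and 13% v 7% dropout, the log odds ratio is 0.00 in adjusted complete case and 0.07 in treatment-only imputation. The planned check does expose this case.

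**Worse than observed (Pearson chi-square, 70 per arm).** Missing = failure moves 38/63 v 25/63 to 38/70 v 25/70: z = 0.1857/0.0841 = 2.21, p = 0.027, across 0.025. It moves 41/63 v 25/63 only from 0.004 to 0.007. For a tipping point, let 3 of 7 missing placebo children respond (28/70). The 38/63 result gives p = 0.018 if 4 of 7 missing OP0201 children respond (42/70) and 0.028 if 3 do (41/70). The 41/63 result crosses 0.025 only if none of the 7 responds.

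**The case against.** The case against rests on weight, and much of it stands.

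- The 38/63 example sits deliberately close to 0.025. That limit binds only when the other endpoint exceeds 0.05; if the other endpoint is below 0.05, only about 0.1% of seeds would turn success into failure at M = 10. The trial-level disagreement of 1.7–5.3% is the fairer measure.
- M = 1 is too improbable to carry weight.
- Leaving covariates out costs about one point of success under random missingness and shrinks the effect towards the null.
- The Day 4 scenario needs arm-differential dropout, which nothing in the documents suggests for a blinded placebo-controlled trial. Even then the shift is about 1 point against a 25-point target.
- A reader could compute an unadjusted missing = failure result from the reported counts, and SAP 16 discloses the change openly.
- Dropping that rule as the primary analysis is defensible. SAP 8.7 excludes otoscopy outside Days 4–6 and 12–14, so a child with a clear ear on Day 15 would be scored as having effusion. In the 13% v 7% scenario the rule errs by 0.7–1.1 points the other way.

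These points limit the size of the problem without removing it. The seed dependence follows from a stated rule and costs almost nothing to cure. A calculation that a reader might do afterwards is no substitute for a pre-specified, covariate-adjusted one.

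**Conclusion.** The concern holds and should be fixed. Three facts rest on the text alone: the imputation count equals the percentage missing with no seed, the imputation model contains treatment group only, and no planned analysis conditions Day 12 on Day 4 status or lets missing outcomes be worse than observed.

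The consequences are modest and mostly confined to near-threshold results. About 2–5% of trials have a seed-dependent verdict, rising to roughly a quarter when the smaller p-value is near the limits. Type I error is preserved under random missingness, and a result of the design size is robust both to the seed and to missing = failure. The seed figures assume 10% missing. The dropout-bias figures rest on assumed correlations and arm-specific dropout rates that the documents do not give, so they show what the planned check could miss and do not predict what will happen.

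**What to change.** In SAP 13.3:

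1. Fix the number of imputations at 100 or more and state the seed. For 140 children 500 is still cheap. Pre-specify any increase near a threshold.
2. Put age stratum, daycare stratum and baseline bulging in the imputation model. Impute Day 12 given Day 4 status, imputing Day 4 first where it is also missing.
3. Pre-specify a simpler fallback for sparse cells: treatment plus baseline bulging for Day 4, treatment plus Day 4 bulging for Day 12.

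In SAP 12.1 and 12.2:

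4. Restore missing = failure as a named sensitivity analysis, described as a bound and not a neutral standard.
5. Add a tipping-point analysis for both primary endpoints.

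The cost is SAP wording, a little programming and a few more tables before unblinding. No new data are needed, and visits and sample size do not change.

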13.4 Multiplicity

The familywise type 1 error rate for the primary efficacy endpoint family will be 0.05 and will be controlled using the Hochberg procedure. Specifically, the p-value of the endpoint with the highest p-value will be compared against the 0.05 significance level and, if significant, both endpoints will be declared significant; if the endpoint with the highest p-value is not significant at the 0.05 level, the other endpoint will be tested at the 0.025 significance level. A positive treatment effect on efficacy will be concluded if at least one of the two endpoints is significant.

Confidential Page 27 of 35

14. SAFETY MONITORING COMMITTEE

An SMC will review blinded safety data for all subjects when approximately 25% of enrolled subjects have completed Day 12 (Visit 3). Safety data will be evaluated on an ongoing basis to ensure it is safe to continue study enrollment and treatment. The composition, responsibilities, and meeting schedule of the SMC will be specified in a charter document.

15. SEQUENCE OF PLANNED ANALYSES

15.1 Final Analysis

The only planned analysis is the final analysis, which will occur after study-level EOS, all clinical data have been entered into the data capture system, AE and concomitant medication data have been coded, quality control checks have been completed, all data queries have been resolved, protocol deviations have been identified, and the database has been locked.

16. CHANGES FROM THE PROTOCOL

Protocol	Change
Primary efficacy analysis to be done using the	ITT population replaced by mITT population
ITT population defined as all randomized	which excludes the first 3 subjects dosed.
subjects.	
Subjects with missing data at the Day 4 Visit	Multiple imputation will be used for missing
will be considered as having bulging TM and	data for the primary efficacy analysis, with a
those with missing data at the Day 12 Visit	complete-case sensitivity analysis added.
will be considered as having MEE.	
GEE will be used for analyses of repeating	All binary endpoints will be analyzed separately
binary endpoints.	by visit using logistic regression.
Secondary efficacy endpoints, which included	Tympanogram findings will not be analyzed
"normal tympanogram," will be statistically	and will be reported as descriptive statistics
analyzed.	only.
Secondary efficacy endpoints will be	Complete-case analyses using the mITT
analyzed using the Safety population.	population will be done for secondary efficacy
	endpoints.

Confidential Page 28 of 35

REFERENCES

- 1. International Conference on Harmonisation of Technical Requirements for Registration of Pharmaceuticals for Human Use, ICH Harmonised Tripartite Guideline, Statistical Principles for Clinical Trials (E9), September 1998.
- 2. American Statistical Association (ASA). (2018) Ethical Guidelines for Statistical Practice. Prepared by the Committee on Professional Ethics, April 2018. http://www.amstat.org/ASA/Your-Career/Ethical-Guidelines-for-Statistical-Practice.aspx.
- 3. International Conference on Harmonisation of Technical Requirements for Registration of Pharmaceuticals for Human Use, ICH Harmonised Tripartite Guideline, Structure and Content of Clinical Study Reports (E3), November 1995.
- 4. International Conference on Harmonisation of Technical Requirements for Registration of Pharmaceuticals for Human Use, ICH Harmonised Tripartite Guideline, Good Clinical Practice (E6), April 1996.
- 5. International Conference on Harmonisation of Technical Requirements for Registration of Pharmaceuticals for Human Use, ICH Harmonised Tripartite Guideline, General Considerations for Clinical Trials (E8), July 1997.
- 6. International Conference on Harmonisation of Technical Requirements for Registration of Pharmaceuticals for Human Use, ICH Harmonised Tripartite Guideline, Statistical Principles for Clinical Trials (E9), September 1998.

APPENDIX A: SCHEDULE OF ACTIVITIES

Procedure	Visit	Screening/ Enrollment Visit 1	Visit 2	Visit 3	Study Exit Visit 4/Early Discontinuation ^f
	Study Day	Day 1	Day 4 (+2)	Day 12 (+2)	Day 28 (±2)
Informed consent		X			
Inclusion/exclusion cri	teria	X			
Demographics		X			
Medical/surgical/ear hi	istory	X			
Baseline otitis media ri	isk factors	X			
AOM-SOS scorea		X	Х	Х	х
Physical examination ^b		X	Х	Х	х
Height and weight		X			
Vital signs (temperatur respiratory rate)	re, pulse and	X	х	х	Х
Pneumatic otoscopy of	each earc	X	X	X	X
Tympanogram of each	earc	X	X	X	X
Endoscopic examination capture of each ear (who using the iPhone application)	nen possible)	X	X	x	X
Randomization to OP0 placebo	201 or	X			
Train parent/caregiver treatment administration		X			
Train parent/caregiver completion of AOM-So daily electronic diary		X			
Nasal saline rinse and/ suction, as neededd	or nasal	X	x	x	х
Observe parent/caregiv first dose of intranasal treatment		X			
Dispense 10-day suppl treatment	y of study	X			
Safety observatione		X			
Check electronic diary, study treatment adherence, AOM-SOS assessment adherence/retrain as needed			X	X	
Concomitant medication	ons	X	X	X	X
Adverse event		X	X	X	X
Device Experience Que	estionnaire			X	Xg

Confidential Page 30 of 35

AOM-SOS = Acute Otitis Media Severity of Symptom

- The AOM-SOS scale is scored by the parent/caregiver once daily at home for the total duration of the antibiotic and study treatment period. At the screening visit the parent/caregiver will be asked to score the AOM-SOS scale as part of the screening criteria for the study. Parents/caregivers must not be informed of the score required to meet study enrollment criteria.
- b Physical examination including visual examination of the nasopharynx and oropharynx at each visit.
- Cotoscopy and tympanometry (when possible) to be performed prior to the first dose of the study treatment on Day 1. When possible, otoscopy and tympanometry to be performed 30 minutes following administration of the first dose of the study treatment on Day 1. Trained otoscopists who have undergone comprehensive educational program (enhancing proficiency in otitis media) for training in the diagnosis of AOM will perform the otoscopy assessments. This training includes training on cerumen removal, which is required (as needed) prior to performing pneumatic otoscopy or tympanogram.
- d Train parent/caregiver on nasal saline rinse and/or nasal suction on Day 1 and remind parent/caregiver of rinse and/or suction during the study treatment period, as needed.
- Safety observation for 30 minutes following administration of the first dose of study treatment.
- f If a Participant exits the study prior to the Day 28 Study Exit visit, all Day 28 final measurements should be performed and recorded on the appropriate eCRF.
- Device Experience Questionnaire should only be completed for all Early Discontinuation Participants if they exit prior to Day 12 and did NOT complete the questionnaire.

Confidential Page 31 of 35

